10.3.3 Method of Pooling Sites to Generate Analysis Centers

Subjects from low enrolling sites will be pooled in order to generate analysis centers. The minimum number of subjects per analysis center is 10. For sites with <10 enrollments, the lowest enrolling site will be combined with the largest enrolling site, and then the second lowest enrolling site and the second largest enrolling site will be combined, and so on. Further combining will be done as necessary until all analysis centers have at least 10 subjects. All analyses that are controlled for site will use this analysis center designation. Site poolability will also be assessed as described in Sections 10.3.1 and 10.3.2. Full details will be provided in the SAP.

10.3.4 Handling of Missing Data for the Co-Primary Efficacy Endpoints in the ITT Population

For both HDSM-Ax-7 and GSP, multiple imputations for missing values in the vehicle group will be performed assuming MAR. For the sofpironium bromide gel, 15% group, multiple imputations using the CBI model will be employed as the primary imputation method to handle missing data. This approach will adopt a missing not at random (MNAR) assumption and missing values in the sofpironium bromide gel, 15%, group will be imputed based on a distribution with estimated values at visits lost to follow-up similar to that of subjects in the vehicle group. This approach further assumes that for the treatment effect observed in sofpironium bromide gel, 15% arm, subjects with missing data gradually trends towards the estimated mean in the vehicle group, i.e., any treatment benefit gained is not immediately lost upon withdrawal. The same co-primary analysis models will be applied to the multiple imputed datasets and the results combined via Rubin's rules (Rubin, 1976).

Furthermore, in order to ensure that the missing data imputation method proposed is robust to outliers for the GSP co-primary endpoint, data from subjects that meet the criterion for being an outlier will be removed from the imputation sampling database as follows. Combining the Vehicle and sofpironium bromide gel, 15% arms, the mean and standard deviation will be calculated for the non-missing GSP change from baseline to EOT data. Data values more than 3 standard deviations away from the mean will be regarded as outliers. However, since the outliers are included in the original mean and standard deviation calculations and would have inflated their values, the outliers will be set aside and the mean and standard deviation will be re-calculated to see if any additional outliers are identified. This process will be repeated until no more outliers are identified. Prior to performing imputation for missing GSP change from baseline data in the ITT population, data values contributing to the outlying observations will be removed from the imputation sampling database, i.e. the non-missing vehicle data. With this approach, outlying data will not be propagated during missing data imputation. Once an imputation is complete, all original non-missing data and the imputed, previously missing data will be used for the GSP ITT analysis. Further details for this approach will be included in the SAP.

10.3.5 Sensitivity Analyses of the Co-Primary Efficacy Endpoints

To further explore the robustness of the primary analysis results to different missing data assumptions, analyses using two additional imputation methods will be performed as presented below. Furthermore, the ranked GSP and non-rank transformed GSP ANCOVA analyses will be repeated without imputing missing data, and again after removing outlier data. Additionally, the 7 items in the HDSM-Ax-7 scale will be analyzed individually to support the primary analysis for this co-primary endpoint.

Summary of Sensitivity Analyses of the Co-Primary Efficacy Endpoints

	Co-Primary Efficacy Endpoint Assessed	Sensitivity Analysis
1	GSP change from baseline to EOT	Analysis performed on available data only without imputing missing data; using both ranked and non-ranked data.
2	GSP change from baseline to EOT	Subjects with outlying data removed from analysis; using both ranked and non-ranked data (multiple imputations for missing data).
3	HDSM-Ax-7 2-point improvement from baseline to EOT	Missing data imputed as failure/non- response (single imputation only)
4	HDSM-Ax-7 2-point improvement and GSP change from baseline to EOT	Tipping point analysis (multiple imputations for missing data)
5	HDSM-Ax-7 2-point improvement from baseline to EOT	Analysis of the 7 individual items in the HDSM-Ax-7 scale (multiple imputations for missing data)

Unless otherwise specified, sensitivity analyses pertain to the primary analyses for the co-primary endpoints only. A brief description of each sensitivity analysis is provided below; complete details will be included in the final SAP.

Sensitivity Analysis 1: To further investigate the robustness of the GSP co-primary efficacy endpoint, the ranked and non-rank transformed GSP analyses will be repeated on all available data only without imputing missing data. The methodology will be similar to the primary analysis of the GSP co-primary endpoint.

Sensitivity Analysis 2: To further investigate the robustness of the GSP co-primary efficacy outcome, the ranked and non-rank transformed GSP analyses will be repeated after removing outlier data (as defined in Section 10.3.4). The methodology will be similar to the primary analysis of the GSP co-primary endpoint, except that outlier data will be removed from the imputed database for these analyses.

Sensitivity Analysis 3: Missing post-baseline HDSM-Ax-7 data will be imputed as failure/non-response in both treatment groups. The co-primary efficacy HDSM-Ax-7 analysis will be re-run on the so-imputed HDSM-Ax-7 dataset and treatment success proportion estimates will be produced.

Sensitivity Analysis 4: A tipping point analysis will be conducted to investigate the robustness of the co-primary efficacy outcomes. Tipping point analyses will be conducted separately for the HDSM-Ax-7 and GSP co-primary endpoints.

For the GSP co-primary endpoint, missing data in the vehicle arm will be assumed to be MAR, while missing data from the sofpironium bromide gel, 15%, arm will be imputed assuming that subjects with missing data have missing GSP data that are worse by a prespecified Δ compared to similar subjects with observed data. Missing

Page 54 of 102

values will be multiply imputed via this method with increasing Δ values. A Δ increment of 5 mg will be used for this study. The GSP co-primary efficacy outcome analysis methodology will be applied to the imputed datasets and repeated until statistical significance no longer holds. The tipping point will be identified and the results will be summarized graphically.

For the HDSM-Ax-7 co-primary endpoint, identical imputation methodology to that described above for the GSP will be applied to the HDSM-Ax-7 total scores, and the resulting values will be dichotomized into responders versus non-responders using the 2-point improvement criterion. A Δ increment of 0.5 (on a 0-4 scale) will be used for this study. The HDSM-Ax-7 co-primary efficacy outcome analysis methodology will be applied to the imputed datasets and repeated until statistical significance no longer holds. The tipping point will be identified and the results will be summarized graphically.

Sensitivity Analysis 5: A sensitivity analysis will be conducted to investigate whether any of the individual items in the HDSM-Ax-7 scale are overly influencing changes observed in the total score. First, a subject will be counted as a responder if they achieve at least a 2-point improvement in the individual question from baseline to EOT. The logistic regression model for the primary analysis for HDSM-Ax-7 will be repeated for each of the 7 individual items, and each individual question will be analyzed separately. Secondly, one of the 7 items will be omitted, and the HDSM-Ax-7 total score will be calculated as the average of the remaining 6 items. The primary logistic regression analysis for 2-point improvement response rate will be performed on this 6-item scale. This process will be repeated 7 times, each time with a different item of the HDSM-Ax-7 scale removed from calculation of the overall score.

10.3.6 Analysis of the Secondary Efficacy Endpoints

A gated, fixed-sequence testing procedure will be used in this protocol to control the overall familywise false positive error rate for the primary and secondary endpoints analyses. As described above, the primary analysis will be regarded as positive and the trial will be successful for the co-primary efficacy endpoints if both null hypotheses in Section 10.3.1 and Section 10.3.2 of no difference are rejected in favor of sofpironium bromide gel, 15% at the 2-sided 0.05 level of significance.

If both co-primary analyses yield statistically significant results in favor of the sofpironium bromide gel, 15% group, the three secondary efficacy endpoints specified in Section 10.2.3 will be tested in a fixed sequence in the order presented in Section 10.2.3. Testing will continue only if all previously tested null hypotheses have been rejected at the 2-sided alpha=0.05 significance level in favor of sofpironium bromide gel, 15%.

The HDSM-Ax-7 1-point improvement responder secondary endpoint analysis will be conducted using the same logistic regression model as that used for the HDSM-Ax-7 co-primary efficacy analysis. For the composite endpoints, both baseline HDSM-Ax-7 score and baseline GSP value will be included as covariates.

10.3.7 Analysis of Exploratory Efficacy Endpoints

PGI-S and PGI-C endpoints will be analyzed using a Cochran-Mantel-Haenszel test. All other exploratory efficacy endpoints that involve a proportion of responders will be analyzed using methods similar to what was described for the HDSM-Ax-7 co-primary endpoint. All other exploratory endpoints that involve a change from baseline to a single timepoint will be analyzed using methods similar to what is described for the GSP co-primary endpoint. P-values for exploratory efficacy endpoints will be provided for descriptive purposes only and no formal hypothesis testing will occur. All exploratory efficacy analyses will be based on available data and missing GSP and HDSM-Ax EOT data imputed.

10.3.8 Psychometric Analysis of the HDSM-Ax-7

In parallel to the traditional statistical analysis, psychometric evaluation of the HDSM-Ax-7 will be carried out to confirm the most appropriate HDSM-Ax-7 scoring algorithm and to examine internal validity, construct validity (i.e., examination of the magnitude of correlation between the HDSM-Ax total score and key variables such as Questions 4 and 5 of the HDSM-Ax-7, PGI-S, PGI-C, and GSP), stability, reliability, ability to detect change, and interpretability of clinical trial results.

The details regarding psychometric analyses will be described in a separate statistical analysis plan.

10.4 Safety Analyses

Safety assessments of interest are local tolerability assessments, AEs, laboratory evaluations, and vital signs.

Safety analysis will be performed by treatment received for the Safety Population. Treatment-emergent adverse event descriptions will be mapped to standard terms, i.e., Medical Dictionary for Regulatory Activities (MedDRA) system organ class and preferred term. At each post-baseline visit, the number and proportion of subjects reporting any given TEAE will be tabulated cumulatively by severity; each subject will be counted only once according to the worst severity reported up to the current visit. Separate tables will be constructed for (a) all reported TEAEs, (b) protocol treatment-related TEAEs, (c) serious TEAEs, (d) TEAEs leading to protocol treatment discontinuation (e) protocol treatment-related serious TEAEs, (f) severe TEAEs, (g) TEAEs leading to dose interruption, (h) TEAEs of special interest, and (i) anticholinergic TEAEs.

At each visit, local tolerability assessments will be descriptively summarized by severity. For any symptoms, subject severity is the worst severity of the two axillae.

An overall summary table will also be presented with subject incidences tabulated according to the worst severity experienced while on study. In addition, at each post-baseline visit, local tolerability will be summarized as cumulative shift tables versus baseline. Subject counts for each symptom will be cross-tabulated with baseline severity according to the maximum post-baseline severity reported for either axilla up to the current visit.

Laboratory parameters will be descriptively summarized (mean, standard deviation, median, minimum, maximum) for values obtained at Visit 1 and Visit 12. Whereas, vital signs will be summarized in a similar manner at each visit.

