Overall, all three sofpironium bromide gel concentrations, 5%, 10%, and 15%, have exhibited a larger absolute mean reduction in gravimetric sweat production (GSP) from baseline to end of treatment (EOT) compared with vehicle. Better improvement in GSP response was associated with higher concentrations of sofpironium bromide. However, while there was a slight trend toward dose response, all gel concentrations were essentially equivalent in patient-reported outcome measures based on the Hyperhidrosis Disease Severity Measure-Axillary (HDSM-Ax), Dermatology Quality of Life Index (DLQI), and Hyperhidrosis Disease Severity Score (HDSS), suggesting that all three concentrations are efficacious. The response was seen as early as Day 8 and remained consistent throughout the applicable treatment period.

Clinical Pharmacokinetics Conclusions

In PK studies conducted to date, both sofpironium and its major metabolite BBI-4010 could be measured in the majority of subjects. Systemic exposure to sofpironium and BBI-4010 appeared to increase in an approximately dose-proportional manner when comparing the 5% and 15% gel concentrations, indicating that applying a more concentrated gel increased exposure. However, inter-subject variability of PK parameters was extremely high. Absorption is thought to be affected by skin thickness, temperature, hydration, and degree of occlusion.

Systemic exposure of sofpironium and BBI-4010 was typically minimal following the first dose (Day 1) and also after multiple doses (Day 21). Sofpironium accumulation after Day 1 was not observed. Plasma concentrations of BBI-4010 appeared to be lower than those of sofpironium. Steady state is likely reached within the first 24 hours. In general, plasma concentrations of sofpironium and BBI-4010 showed most samples analyzed were below 1 ng/mL, with many below the lower limit of quantification of 0.05 ng/mL for both sofpironium and BBI-4010.

Risk to Subjects

As an anticholinergic drug, administration of sofpironium bromide gel could be associated with signs or symptoms typical of anticholinergic effect such as dry mouth, blurred vision, dizziness, constipation, urinary retention, or tachycardia. The previous sofpironium bromide exposure to humans has demonstrated a low incidence of these effects, which are generally mild in severity. All such effects have been observed, and as expected, to be transient.

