8.1.3 Clinical Laboratory Assessments

Hematology, clinical chemistry, urinalysis, and additional parameters to be tested are listed below:

Hematology

Trematorogy		
Platelet count	RBC Indices:	Automated WBC Differential:
Red blood cell (RBC) count	Mean corpuscular volume (MCV)	Neutrophils
White blood cell (WBC) count	Mean corpuscular hemoglobin (MCH)	Lymphocytes
Reticulocyte count	Mean corpuscular hemoglobin concentration (MCHC)	Monocytes
Hemoglobin		Eosinophils
Hematocrit		Basophils

Clinical Chemistry

Blood urea nitrogen	Chloride	Alkaline phosphatase
Creatinine	Aspartate aminotransferase (AST)	Total and direct bilirubin
Sodium	Alanine aminotransferase (ALT)	
Potassium	Gamma glutamyl transferase (GGT)	

Routine Urinalysis

Bilirubin, color, appearance, glucose, ketones, leukocyte esterase, nitrite, occult blood, pH, protein, specific gravity, and urobilinogen

Microscopic examination (if blood or protein is abnormal)

Other Screening Tests

Urine Pregnancy Test (females of childbearing potential* only, using UPT tests provided by the Sponsor.)

^{*} Females of childbearing potential for this study includes any female capable of becoming pregnant who has not undergone successful surgical sterilization (hysterectomy, bilateral tubal ligation [≥6 months prior to baseline], or bilateral oophorectomy) or is not postmenopausal (defined as amenorrhea ≥12 consecutive months).

All results will be reported and must be reviewed by the Investigator or designee. Abnormal results shall be assessed for clinical significance. Repeat laboratory testing may be requested at the discretion of the Investigator. If an AE should require laboratory testing, the results of the test should be obtained by the investigative site and filed in the subject's documentation.

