9.2 Adverse Events

9.2.1 Definitions of Adverse Events

According to 21 CFR Parts 312.32 and 320.32 (IND Safety Reporting, Applicability of Requirements Regarding an "Investigational New Drug Application"), Food and Drug Administration (FDA) Guidance for Industry (Investigational New Drug Safety Reporting Requirements for Human Drug and Biological Products and Safety Reporting Requirements for Bioavailability and Bioequivalence Studies in Humans) (Federal Register/Vol. 75, No. 188/September 29, 2010) and International Council on Harmonisation (ICH) E2A (Clinical Safety and Data Management: Definitions and Standards for Expedited Reporting):

An adverse event (AE) means any untoward medical occurrence associated with the use of a drug in humans, whether or not considered drug related.

A suspected adverse reaction (SAR) means any AE for which there is a reasonable possibility that the drug caused the AE.

The following information should be considered when determining whether or not to classify a test result, medical condition, or other incident as an AE:

Adverse events will be recorded from the time of informed consent.

Abnormal laboratory values should not generally be recorded as AEs unless an intervention is required, the laboratory abnormality results in an SAE, the lab abnormality results in study termination or interruption/discontinuation of study treatment, or the lab abnormality is associated with clinical signs or symptoms. When recording an AE resulting from a laboratory abnormality, the resulting medical condition rather than the abnormality itself should be recorded (e.g., record "anemia" rather than "low hemoglobin").

Complications that occur in association with a protocol-mandated intervention (e.g., invasive procedures such as biopsies) should be recorded as AEs.

Whenever possible, the Investigator should group signs or symptoms that constitute a single diagnosis under a single event term. For example, cough, rhinitis, and sneezing might be grouped together as "upper respiratory tract infection." If possible, abnormal laboratory results that meet the definition of an AE (see above) should be reported as a clinical diagnosis rather than the abnormal value itself (e.g., "anemia" rather than "decreased blood count").

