## 9.4 Clinical Laboratory Evaluation

Safety laboratory parameters (hematology, chemistry, urinalysis) will be collected at the Screening Visit and EOT Visit. Urine pregnancy results will be collected at visits 1, 4, 8, and 12 (EOT). Laboratory parameters will be presented in Systeme International (SI) units and descriptively summarized for values at each visit and for changes from baseline at each subsequent visit. Unscheduled visits and early termination visits will be included.

Laboratory parameters to be summarized and listed include hematology, clinical chemistry, and routine urinalysis. Urine pregnancy test results will be listed only.

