# 9.5 Vital Signs, Physical Findings, and Other Observations Related to Safety

## 9.5.1 Vital Signs

Vital signs measurements will be collected at Visits 4, 5, 6, 7, 8, 9, 12 (EOT), and 13 (follow-up). Visit 4 data are the Baseline. Should Visit 4 data be missing, baseline will be derived as the last value prior to first dose (e.g. Screening), and, as such, unscheduled visits may be included. Vital sign measurements will include systolic and diastolic blood pressure, pulse rate, respiratory rate, and temperature. Vital sign parameters will be descriptively summarized for values at each visit and for changes from baseline at each subsequent visit. Vital signs will also be listed.

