| 14.3.1.8.9  | Number and Percentage of Subjects with
Anticholinergic Treatment-Emergent Adverse Events
Cumulative to Visit 13 (Day 57, Follow-up) by System
Organ Class, Preferred Term, and Maximum Severity     | Safety     |
| 14.3.1.8.10 | Number and Percentage of Subjects with Local Site
Reaction Treatment-Emergent Adverse Events
Cumulative to Visit 14 (Day 57, Follow-up) by System
Organ Class, Preferred Term, and Maximum Severity | Safety     |
| 14.3.1.9    | Summary of Subjects with Allergic Contact Dermatitis   | Safety     |
| 14.3.4.1    | Mean and Mean Change from Baseline in Serum
Biochemistry Values by Visit  | Safety     |
| 14.3.4.2    | Mean and Mean Change from Baseline in Hematology
Values by Visit  | Safety     |
| 14.3.4.3    | Mean and Mean Change from Baseline in Continuous
Urinalysis Values by Visit   | Safety     |
| 14.3.4.4    | Categorical Urinalysis Values by Visit   | Safety     |
| 14.3.5      | Study Drug Administration Exposure and Compliance  | Safety     |
| 14.3.6.1    | Worst Post-baseline Severity for Local Tolerability
Assessments by Treatment Group  | Safety     |
| 14.3.6.2    | Worst Severity for Local Tolerability Assessments by
Treatment Group and Visit  | Safety     |
| 14.3.6.3    | Shift in Worst Severity for Local Tolerability
Assessments from Baseline to Each Visit  | Safety     |
| 14.3.6.4    | Mean and Mean Change from Baseline in Vital Signs
Values by Visit   | Safety     |
| 14.3.6.5    | Summary of Concomitant Medications by Drug Class
and Generic Drug Name  | Safety     |

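### Apart from categorical urinalysis and events reported as AEs, no planned table counts subjects by arm with an abnormal or shifted pulse, hematology or chemistry value

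*Protocol*

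**What the plan says.** Protocol 10.4: "Laboratory parameters will be descriptively summarized (mean, standard deviation, median, minimum, maximum) for values obtained at Visit 1 and Visit 12". The next sentence extends this to vital signs: "Whereas, vital signs will be summarized in a similar manner at each visit".

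SAP 9.5.1: "Vital sign parameters will be descriptively summarized for values at each visit and for changes from baseline at each subsequent visit". SAP 9.4 has laboratory parameters "descriptively summarized for values at each visit and for changes from baseline at each subsequent visit".

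The list in SAP 15 agrees. Tables 14.3.4.1 (chemistry), 14.3.4.2 (hematology), 14.3.4.3 (continuous urinalysis) and 14.3.6.4 (vital signs) share one form of title, of which the last is typical: "Mean and Mean Change from Baseline in Vital Signs". Table 14.3.4.4 covers categorical urinalysis by visit. Individual results are in Listings 16.2.8.1 to 16.2.8.3 and 16.2.9.2.

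On risk, protocol section 1 says the drug could be associated with anticholinergic signs or symptoms such as "dry mouth, blurred vision, dizziness, constipation, urinary retention, or tachycardia". SAP 2.1 places safety and local tolerability under its primary objectives.

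On the AE route, protocol 9.2.1 says: "Abnormal laboratory values should not generally be recorded as AEs unless an intervention is required". It then gives further conditions: the abnormality results in an SAE, leads to study termination or to interruption or discontinuation of treatment, or comes with clinical signs or symptoms. Protocol 9.6 leaves it optional whether clinically significant changes in vital signs or laboratory tests are recorded as AEs. Protocol 8.1.3 says of laboratory results: "Abnormal results shall be assessed for clinical significance".

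**The concern.** Pulse is measured at eight visits (4 to 9, 12 and 13), and hematology and chemistry before and at the end of treatment. The plan reduces these to group statistics at each visit. It defines no pulse category, no low/normal/high laboratory category and no shift table for them. SAP 9.3 does use worst-severity counts and shift tables, but only for local tolerability.

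An effect confined to a few subjects barely moves an arm mean. A maximum shows that an extreme value occurred, not how many subjects had one or at how many visits. The protocol describes between-subject variability in pharmacokinetics as very large, although it also reports that exposure was typically minimal. An effect limited to a subset is therefore a reasonable pattern to provide for. At stake is whether the planned safety tables answer a direct question: how many subjects in each arm had a marked pulse rise or left the laboratory normal range?

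**Working it through.** The plan gives no figure on this point, so there is nothing to reproduce. The check has three parts.

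**1. What each output can show**

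| Data | Planned table | Subject count by arm on the measured value? |
|---|---|---|
| Chemistry, hematology, continuous urinalysis | 14.3.4.1 to 14.3.4.3, mean and mean change | No |
| Categorical urinalysis | 14.3.4.4, by visit | Yes, by category; no shift |
| Pulse and other vital signs | 14.3.6.4, mean and mean change | No |
| Anything recorded as a TEAE | 14.3.1.x, by preferred term and highest severity, including an anticholinergic table | Yes, if recorded |
| Investigator's clinical-significance assessment (protocol 8.1.3) | None listed | No |

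The AE rows catch only what is recorded. Protocol 9.6 makes recording optional, protocol 9.2.1 restricts it for laboratory values, and protocol 8.1.4 prefers open-ended questioning, under which an asymptomatic pulse rise may not surface. Tachycardia is not among the TEAEs of special interest in SAP 9.2, and the SAP gives no preferred-term list for anticholinergic TEAEs.

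**2. How much a subset moves the mean (illustration)**

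From the documents: 175 subjects per arm (protocol section 2). Assumed: a fraction f of the active arm rises by 30 bpm, and the SD of pulse change is otherwise 8 to 12 bpm in both arms.

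- Mean shift = f × 30.
- Active-arm variance = SD² + f(1 − f) × 30².
- SE of the arm difference = √[(SD² + active-arm variance)/175].

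| f | Subjects | Mean shift (bpm) | SE (bpm), SD 8 to 12 | Shift ÷ SE |
|---|---|---|---|---|
| 2% | 3.5 | 0.6 | 0.91 to 1.32 | 0.66 to 0.45 |
| 5% | 8.8 | 1.5 | 0.99 to 1.37 | 1.52 to 1.09 |
| 10% | 17.5 | 3.0 | 1.09 to 1.45 | 2.75 to 2.07 |

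Means begin to show the effect at about 10% affected. The weak spot is smaller subsets.

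**3. How much noise a count table would carry**

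Take, only to test the idea, a flag for any rise of at least 20 bpm from baseline. With normal changes of mean zero, the per-visit probability is p = P(Z ≥ 20/SD): 0.0062, 0.0228 and 0.0478 for SD 8, 10 and 12.

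- Any of the seven post-baseline visits (5 to 9, 12, 13), visits independent: 175 × [1 − (1 − p)⁷] = about 8, 26 and 51 subjects per arm.
- On-treatment visits only (5 to 9, 12): 175 × [1 − (1 − p)⁶] = about 6, 23 and 45.
- At least two of those six visits: 175 × [1 − (1 − p)⁶ − 6p(1 − p)⁵] = about 0.1, 1.3 and 5.3.

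Independence is the extreme case. A simulation with equal between-visit correlation of 0.5 to 0.7 gives about 5 to 6, 14 to 19 and 27 to 34 for the seven-visit rule. For two of six visits it gives about 1, 5 and 11 to 12, so repetition still helps but less. The form of the pulse criterion therefore matters as much as having one.

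**The case against.** Three stronger readings are tempting, and the documents do not support them.

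- *A reader might infer that these subjects are counted nowhere.* Tachycardia or a laboratory abnormality recorded as a TEAE is counted by arm, preferred term and severity. There is an anticholinergic TEAE table at seven visits, and categorical urinalysis has its own table. The conditions in protocol 9.2.1 also bring the more consequential laboratory abnormalities into the AE tables.
- *A reader might infer that the report could not give the counts.* The values are listed, so counts can be recovered, and SAP section 1 allows supplementary analyses after database lock. Table specifications are in a separate document that was not available here, so table content is read from titles and SAP text.
- *A reader might expect a count table to isolate the affected subjects, with none on vehicle.* Part 3 of the working shows otherwise. A single-visit rise criterion could flag dozens of subjects per arm by chance and would itself hide a handful of true cases.

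It is also fair that the restriction in protocol 9.2.1 concerns laboratory values and gives no reason for the AE tables to miss tachycardia. For pulse the gap rests on the optional wording of protocol 9.6. The protocol's account of earlier studies reports a low incidence of systemic anticholinergic events, and no cut-off for pulse has a source in the documents.

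These points narrow the concern without removing it. A listing is not a by-arm summary, and an analysis added after lock can be chosen with the results in view.

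**Conclusion.** The point holds in limited form. Followed as written, the plan produces no by-arm count of subjects with an abnormal or shifted measured pulse, hematology or chemistry value unless the finding was recorded as an AE. That is a weak display for a primary safety objective and a named risk. No stated figure, efficacy result or AE table is wrong because of it, and sample size and alpha are untouched. It is a cheap improvement to the safety outputs.

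The size is illustrative: with 2% to 5% of an arm affected, the mean shift is about 0.5 to 1.5 standard errors of the arm difference. This rests on an assumed 30 bpm rise and an assumed SD of change of 8 to 12 bpm, neither of which comes from the documents. The chance-flag counts also assume normal changes centred on zero.

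**What to change.** **SAP 9.4.** Add low/normal/high shift tables by arm, baseline to EOT, for hematology and chemistry. Add the number of subjects by arm whose EOT value the investigator judged clinically significant, where that assessment is captured in the database.

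**SAP 9.5.1.** Add one table by arm with n (%) of subjects meeting a categorical pulse criterion at the on-treatment visits (5 to 9 and 12). Show Visit 13 separately, because it falls two weeks after treatment ends. Preferably require both a value above an age-appropriate limit and a rise from baseline, or require the criterion at more than one visit, to limit chance flags. Enrolment starts at age 9, so one limit for all ages is unlikely to serve. The sponsor should set these analysis cut-offs and record them before unblinding.

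**Cost.** About three more tables and some SAP wording, from data already collected, with no new procedure. Some subjects in both arms will be flagged by chance, so a footnote should say that the pulse table is descriptive and is to be read as a comparison between arms.
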